6.5.4 Derivation of ≥4 Point and Any Improvement in WI-NRS and AI-NRS

The proportion of subjects with \geq 4 point and any improvement (\geq 1 point) in WI-NRS and AI-NRS from Baseline will be derived from the weekly averages containing at least one daily score and at least 4 daily scores (as discussed in section 6.5.3 for primary and sensitivity analyses, respectively) and will be presented for each week (Weeks 1 to 8).

6.5.5 Percent Change from Baseline

Percent change from Baseline will be derived for continuous (WI-NRS, AI-NRS) endpoints and for the total score for ordinal endpoints (IGA, EASI, 5-D Pruritus Scale, POEM). Percent change from Baseline will be derived as: [(Post-Baseline value – Baseline value) / Baseline value] * 100.

STATISTICAL ANALYSIS PLAN

Version 3.0 12-Jan-22

For EASI, percent change from Baseline will be derived to indicate subjects who have obtained 50%, 75%, and 90% improvement.

6.5.6 Rescue Medication During Treatment Period

The treatment period (also referenced as "on-treatment") begins on date of subject's first dose and ends on Day of Visit 4 - 1, even if the subject has applied IP on Day of Visit 4.

Based on recorded use of rescue medication the following variables will be derived and normalized as described in section 7.5.4 for all subjects:

- Number of days in a month with rescue treatment (for Week 1 to Week 4 and Week 5 to Week 8)
- Number of days every 2 weeks with rescue treatment (for Day -14 to -1 for Baseline, Day 1 to Day of Visit 3 -1 for Week 2, Day of Visit 3 to Day of Visit 4 -1 for Week 4, Day of Visit 4 to Day of Visit 4 + 13 for Week 6, and Day of Visit 4 + 14 to Day of Visit 5 1 for Week 8)

Proportion of subjects with rescue treatment, and the above two variables (number of days in a month with rescue treatment and number of days every 2 weeks with rescue treatment) will be derived and normalized for subjects with recorded use of rescue medication.

6.5.7 Missing Start and Stop Dates for Prior and Concomitant Medication

Start date:

- If start date is completely missing, start date will be imputed with the informed consent date.
- If year is present and month and day are missing, set month and day to January 1.
- If year and day are present and month is missing, set month and day to January 1.
- If year and month are present and day is missing, set day to the 1st day of month.

Stop date:

- If end date is completely missing, end date will not be imputed and medication will be assumed to be ongoing.
- If year is present and month and day are missing, set month and day to December 31st.
- If year and day are present and month is missing, set month and day to December 31st.
- If year and month are present and day is missing, set day to the last day of month.

6.5.8 Safety Parameters

Safety and tolerability endpoints will consist of all adverse events (AEs) reported during the study duration from the date of randomization through Week 8 (End of Study Visit). Specific AEs are defined below.

STATISTICAL ANALYSIS PLAN

Version 3.0 12-Jan-22

Treatment-Emergent Adverse Events (TEAE): Any AE with onset after the first dose of study medication through 28 days after the last dose of study medication.

Serious Adverse Event (SAE): An AE occurring at any dose that results in any of the following outcomes: death, a life-threatening AE, in-patient hospitalization or prolongation of existing hospitalization, a persistent or significant disability/incapacity, or a congenital anomaly/birth defect.

Associated with Use of the Study Drug: There is a reasonable possibility that the experience may have been caused by the study drug. If the Investigator does not know whether or not study drug caused the event, then the event will be handled as "related to study drug" for reporting purposes. The determination of whether an AE is related to study drug is as follows:

- Related: The AE has a missing, unknown, possible, probable or definite relationship to the study medication.
- Not related: The AE is unlikely or definitely unrelated to the study drug.

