13.2 Definition of a SAE

A serious adverse event is any untoward medical occurrence that, at any dose:

- a) results in death.
- b) is life-threatening.

NOTE: The term 'life-threatening' in the definition of 'serious' refers to an event in which the participant was at risk of death at the time of the event. It does not refer to an event, which hypothetically might have caused death, if it were more severe.

c) requires hospitalization or prolongation of existing hospitalization.

NOTE: In general, hospitalization signifies that the participant has been detained (usually involving at least an overnight stay) at the hospital or emergency ward for observation and/or treatment that would not have been appropriate in the physician's office or out -patient setting. Complications that occur during hospitalization are AEs. If a complication prolongs hospitalization or fulfills any other serious criteria, the event is serious. When in doubt as to whether "hospitalization" occurred or was necessary, the AE should be considered serious. Routine hospitalizations or elective surgeries are generally not regarded as SAEs.

d) results in disability/incapacity

NOTE: The term disability means a substantial disruption of a person's ability to conduct normal life functions. This definition is not intended to include experiences of relatively minor medical significance such as uncomplicated headache, nausea, vomiting, diarrhea, influenza, and accidental trauma (e.g. sprained ankle) which may interfere or prevent everyday life functions but do not constitute a substantial disruption.

- e) is a congenital anomaly/birth defect
- f) Medical or scientific judgment should be exercised in deciding whether reporting is appropriate in other situations, such as important medical events that may not be immediately life-threatening or result in death or hospitalization but may jeopardize the participant or may require medical or surgical intervention to prevent one of the other outcomes listed in the above definition. These should also be considered serious. Examples of such events are invasive or malignant cancers, intensive treatment in an emergency room or at home for allergic bronchospasm, blood dyscrasias or convulsions that do not result in hospitalization, or development of drug dependency or drug abuse.

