13.6 Pregnancy

Any pregnancy that occurs in a female participating in the study must be reported to the Safety Team or to a designated Safety email or fax number provided by the Safety Team within 24 hours of learning of the pregnancy. Follow-up must occur to determine the outcome of the pregnancy (including premature termination) and the status of mother and child. Pregnancy complications and elective terminations for medical reasons must be reported as AEs or SAEs. Spontaneous abortions must be reported as an SAE.

Any SAE occurring in association with a pregnancy and considered by the Investigator as related to the investigational product must be promptly reported to the Sponsor, even if the event occurred after the participant completed the study.

The Investigator must attempt to collect pregnancy information on any female partners of male participants who become pregnant while the male participant is enrolled in the study. Pregnancy information must be reported to the Sponsor as described above.

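### SAP 6.5.8 leaves important medical events and spontaneous abortion out of its SAE definition; applied as written, it would drop such events from the SAE endpoint and TESAE tables

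*SAP*

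**What the plan says.** Protocol 13.2 sets out seriousness under six lettered criteria. The first five are death, threat to life, hospitalization or its prolongation, disability or incapacity, and congenital anomaly. The sixth, (f), asks for medical or scientific judgment about other situations, "such as important medical events that may not be immediately life-threatening or result in death or hospitalization but may jeopardize the participant", and concludes: "These should also be considered serious". Its examples include invasive or malignant cancers and "intensive treatment in an emergency room or at home for allergic bronchospasm, blood dyscrasias or convulsions that do not result in hospitalization". Protocol 13.5.1 names Section 13.2 as the place where seriousness is defined. Protocol 13.6 adds a separate instruction: "Spontaneous abortions must be reported as an SAE".

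SAP 6.5.8 gives its own definition. It names death and a life-threatening event, and the rest of the list reads "in-patient hospitalization or prolongation of existing hospitalization, a persistent or significant disability/incapacity, or a congenital anomaly/birth defect". No further item follows.

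SAE incidence is a safety endpoint in both documents (Protocol 4.2, SAP 3.2.4). SAP 7.5.2 plans separate tabulations of treatment-emergent SAEs. SAP 7.7 lists the departures from the protocol's planned analyses, and the SAE definition is not among them.

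**The concern.** The two documents define the same endpoint differently, and the SAP's version is the narrower. By the protocol's own examples, a convulsion or a blood dyscrasia can be serious without meeting any of the SAP's five outcomes. So can a spontaneous abortion.

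A programmer who took 6.5.8 as the rule for selecting SAEs would leave such events out of three places: the TESAE rows of Table 14.3.1, the TESAE table by system organ class and preferred term (14.3.2.1), and the TESAE table by relationship (14.3.2.2). The reported SAE incidence would then answer a narrower question than the protocol asks, and nothing in SAP 7.7 would alert the reader.

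**Working it through.** The plan gives no figure to reproduce here. The check is a comparison of texts, followed by a trace of the term through the SAP.

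**Step 1. Criteria side by side.**

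| Criterion | Protocol | SAP 6.5.8 |
|---|---|---|
| Death | 13.2 (a) | listed |
| Life-threatening | 13.2 (b) | listed |
| Hospitalization or prolongation | 13.2 (c) | listed |
| Disability/incapacity | 13.2 (d) | listed |
| Congenital anomaly/birth defect | 13.2 (e) | listed |
| Important medical event | 13.2 (f) | not listed |
| Spontaneous abortion | 13.6 | not listed |

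The protocol has six criteria and the SAP five, so 6 − 5 = 1 criterion is missing, plus one event type that the protocol makes serious by a direct instruction.

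**Step 2. Is the SAP list closed?** Its wording requires one of the outcomes it names, and it has no residual category. An event that meets only (f) therefore fails the definition.

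**Step 3. Is (f) restored elsewhere in the SAP?** SAP 3.2.4 and 7.5.2 use the term without redefining it. The footnote to Table 14.3.2.1 only expands the abbreviation. SAP 7.7 is silent. Section 6.5.8 is the only SAP definition in the text supplied.

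**Step 4. Which source feeds the tables?** Two readings are open.

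- Under the first, 6.5.8 is an operating rule. It sits in Section 6.5, which is about derived and transformed data. Its neighbours, the treatment-emergent window and the grouping into related and not related, are working derivations. SAP 5.1 says the final analysis follows the SAP. Events serious only under (f) or 13.6 are then left out.
- Under the second, 6.5.8 is descriptive and the tables use seriousness as the investigator recorded it under Protocol 13.2. Listing 16.2.7.1 shows a Serious field (yes/no) and an SAE criteria field. The events are then counted.

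No sentence in the SAP chooses between these.

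**Step 5. What remains visible on the first reading?** An affected treatment-emergent event would still be counted in Tables 14.3.1.1 to 14.3.1.3 and shown in Listings 16.2.7.1 and 16.2.7.2. What is lost is its count as serious in the summary tables.

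**The case against.** The strongest reply is that seriousness is assigned by the investigator and not by the table programmer. Protocol 13.5.1 ties it to Section 13.2, including (f), and Protocol 13.7 sends each SAE to the sponsor on a signed form. The 13.6 sentence is itself a reporting instruction, so a spontaneous abortion should enter the data already marked as serious. SAP 6.5.8 spells out how relatedness categories are grouped but gives no such algorithm for seriousness, and SAP Section 2 refers the reader to the protocol and eCRFs for study details. On this view the five-item list is loose drafting with no effect on any count.

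That reply stands as far as the consequence goes: the documents do not establish that any event will be lost, so the effect has to be stated conditionally. It does not remove the discrepancy. Either the tables drop protocol SAEs, or the SAP prints a definition that its own tables do not follow.

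A reader might also draw stronger conclusions, which the documents do not support:

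- *That the study stopping rule is affected.* SAP 4.2 repeats the rule, but it acts during conduct on events reported and judged related to treatment. The SAP governs one analysis after database lock, with no interim reporting planned (SAP 5.1). A definition used for tables made after lock cannot change that count.
- *That the SAP narrows disability by calling for persistence or significance.* The protocol's own note under (d) already requires a substantial disruption of normal life functions, so the SAP wording is not shown to be stricter.
- *That SAE counts would disagree with a sponsor safety database.* Neither document describes such a database or a reconciliation with it.
- *That any allergic reaction seen in an emergency room is lost.* The protocol's example is confined to intensive treatment for allergic bronchospasm.

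**Conclusion.** The point holds in conditional form. SAP 6.5.8 conflicts with the governing definition in Protocol 13.2 by omitting one of six criteria, and it does not cover spontaneous abortion under 13.6. The difference is undeclared. Applied literally, it would understate the SAE incidence endpoint and the TESAE tables by exactly those events that are serious only under (f) or 13.6.

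The numerical effect cannot be estimated, because the documents give no expected SAE rate and no share of SAEs arising under (f). It is zero if the tables use the recorded flag, and zero if no such event occurs. The conclusion rests on two assumptions: that nothing outside the supplied text, such as programming specifications, restores (f), and that investigators record seriousness under Protocol 13.2. Since a named safety endpoint is involved and the correction is small, it should be made.

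**What to change.** In SAP 6.5.8, replace the list of outcomes with a definition by reference: an SAE is any AE that is serious under Protocol 13.2 (a) to (f), or a spontaneous abortion under Protocol 13.6. Add one sentence saying that the TESAE rows of Table 14.3.1 and Tables 14.3.2.1 and 14.3.2.2 select events by the investigator-recorded Serious flag shown in Listing 16.2.7.1, and not by re-deriving seriousness from a list of outcomes.

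If the narrower definition was intended, it should instead be declared and justified in SAP 7.7.

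The cost is one or two sentences in the SAP. No new data are needed, because the listing already carries the flag and the SAE criteria. Tables already programmed from the flag need no change.

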6.5.9 Missing Start and Stop Dates for Adverse Events

Start date:

- If start date is completely missing, start date is set to date of first dose.
- If (1) year is present and month and day are missing or (2) year and day are present and month is missing:
 - If year = year of first dose, then set month and day to month and day of first dose.
 - If year < year of first dose, then set month and day to December 31st.
 - If year > year of first dose, then set month and day to January 1st.
- If month and year are present and day is missing:
 - If year = year of first dose and
 - If month = month of first dose, then set day to day of first dose date.
 - If month < month of first dose, then set day to last day of month.
 - If month > month of first dose, then set day to 1st day of month.
 - If year < year of first dose, then set day to last day of month.
 - If year > year of first dose, then set day to 1st day of month.

Stop date:

If the outcome of the AE was ongoing or unknown, then the rules outlined below will not be applied.

- If stop date is completely missing, stop date is set to date of study discontinuation/end of study date.
- If (1) year is present and month and day are missing or (2) year and day are present and month is missing:
 - If year = year of study discontinuation, then set month and day to month and day of study discontinuation.
 - If year < year of study discontinuation, then set month and day to December 31st.

STATISTICAL ANALYSIS PLAN

Version 3.0 12-Jan-22

- If year > year of study discontinuation, then set month and day to December 31st.
- If month and year are present and day is missing:
 - If year = year of study discontinuation/end of study date and
 - If month = month of study discontinuation/end of study date, then set day to day of study discontinuation date.
 - If month < month of study discontinuation/end of study date, then set day to last day of month.
 - If month > month of study discontinuation/end of study date, then set day to 1st day of month.
 - If year < year of study discontinuation/end of study date, then set day to last day of month.
 - If year > year of study discontinuation/end of study date, then set day to 1st day of month.

6.5.10 Visit Windows

It is expected that all visits should occur according to the protocol schedule. All visit data will be tabulated per the evaluation visit as recorded on the CRF even if the assessment is outside of the visit window. All ePRO/diary data will be tabulated per the weekly conventions defined in Section 6.5.3. In data listings, the relative day of all dates will be presented.

6.5.11 Categorization of Continuous Variables

For reporting and analysis purpose continuous variables may be categorized.

Age at Baseline will be categorized in 3 groups: 18 to 40 years, 41 to 54, 55 to 65 years.

BSA will be categorized in 3 groups: 10 to 20%, >20 to 30%, >30 to 40%. If subjects are admitted into the study with baseline BSA outside of these specified ranges, then the subject will be placed into the closest occurring category. For example, if a subject is admitted into the study with a baseline BSA of 50%, then they will be included in the >30-40% category. Footnotes will be added to relevant tables, listings, or figures (TLFs) noting how many subjects out of range were included in the analysis.

6.5.12 Site Related Baseline Covariates

Site may be included as a covariate in regression models. Additional covariates reflecting site, seasonality, and geographical variation may be derived and included in sensitivity analyses.

For pooling of sites, the following covariates may be defined:

- Enrollment low to high (for example, pool by number of subjects enrolled: 1-9, 10-15, 16-25, 26+)
- Enrollment gap (based on time between enrolled patients, one or more gaps of 56 days or above between enrollment v none)

STATISTICAL ANALYSIS PLAN

Version 3.0 12-Jan-22

For investigation of seasonality and geography effect the following covariates on site level will be defined:

- Colder v warmer months (randomized Oct. Mar / Apr Sep)
- Seasonal geographic locations (warm all year v cooler all year)

For IP effect the following covariates may be defined:

• IP lot used (subjects who use at least 2 kits from the same lot can be included in the lot analysis)

Above mentioned site related baseline covariates may be derived if post-hoc analyses are performed (see Section 7.4).

7 STATISTICAL ANALYSES

7.1 Sample Size Determination

Approximately 576 subjects may be enrolled to account for 16.7% drop out rate prior to completing the study. A total of 160 evaluable subjects per group (480 total) are required to achieve at least 80% power to detect a pairwise difference of 0.65 in mean WI-NRS change from Baseline to Week 4 between one of two active doses of B244 and vehicle control when assuming a standard deviation of 2.5 and applying a Dunnett Testing Method at a one-sided familywise error rate of 0.10.

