	Day 14 (Week 2) and Day 28 (Week 4). All subjects will be asked to attend a
	Week 8 follow-up visit 4 weeks (28 days (±3) days) after the last dose of study
	medication.
Statistical Considerations:	Sample Size:
	Approximately 576 subjects may be enrolled to account for 16.7% drop out rate prior to completing the study.
	A total of 160 evaluable subjects per group (480 total) are required to achieve
	at least 80% to detect a pairwise difference of 0.65 in mean WI-NRS change
	from baseline to Week 4 between one of two active doses of B244 and vehicle
	control when assuming a standard deviation of 2.5 and applying a Dunnett

Testing Method at a one-sided familywise error rate of 0.10.

Populations:

- ITT population: All subjects who are enrolled and apply at least 1 dose of study treatment will be included in the Intent to Treat (ITT) population. The ITT population will be the primary population for safety and efficacy assessments.
- Per Protocol (PP) population: All subjects in the ITT population without any protocol deviations that may have an impact on the efficacy assessments, who complete their Week 4 visit, and who administer at least 50% of investigational product (IP), will be included in the Per Protocol (PP) population.
- Safety Population: All subjects treated with at least one dose of IP.

Efficacy Analysis:

Efficacy analysis will be performed on the ITT population with some supportive analysis on the PP population. Regression models will include all eligible subjects for the respective analysis, from the 3 treatment arms.

Hypothesis tests for the primary efficacy endpoint will be performed using a Dunnett Testing Method, applying pairwise comparisons of each respective B244 dose group to vehicle using a one-sided familywise error rate of 0.10. No additional adjustments will be made for multiple testing.

Additional supportive analyses may be performed combining the B244 dose groups in comparison against vehicle and comparison of the B244 groups to one another.

The frequency and rate of NRS responders at Week 4 (≥4 point change from baseline in NRS) will be reported and compared between treatment groups using a logistic regression model.

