6 SELECTION OF STUDY PARTICIPANTS

6.1 Number of Participants Planned

Approximately 576 subjects (192 per treatment group) with pruritus and a history of atopic dermatitis will be randomized into this study.

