11.6 Study Completion

A completed participant is one who has completed all study visits. Day 56 study visit is defined as the participant's last visit.

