7.2.6 Role of Populations in Analyses

The results in the mITT population will be considered definitive for superiority of each active treatment to vehicle with those in the PP population considered supportive. Safety analyses will be performed using the Safety population.

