The ANCOVA model for the primary endpoint change from Baseline to Week 4 in weekly average WI-NRS will have treatment group and Baseline weekly average WI-NRS as explanatory variables. Hypothesis testing will be done using a Dunnett Testing Method, applying pairwise comparisons of each respective B244 dose group to vehicle using a one-sided familywise error rate of 0.10. Treatment effect will be estimated as least squares means using vehicle as reference and adjusted for multiplicity according to the Dunnett Testing Method and presented with one-sided 90% CI.

Additionally, the two B244 dose groups will be compared by presenting the treatment difference estimated using least squares means.

Finally, in a separate analysis, the pooled B244 dose groups will be compared to vehicle using the same ANCOVA model.

STATISTICAL ANALYSIS PLAN

Version 3.0 12-Jan-22

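### On its stated inputs, 160 evaluable subjects per arm give about 77% power for a given B244 dose against vehicle, not the stated 80% or more; 80% needs 174 per arm

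*SAP*

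**What the plan says.** SAP 7.1 and Protocol 12.1 carry the same sentence. It says that 160 evaluable subjects per group, 480 in total, are "required to achieve at least 80% power to detect a pairwise difference of 0.65 in mean WI-NRS change" from Baseline to Week 4, for one of the two B244 doses against vehicle, "when assuming a standard deviation of 2.5 and applying a Dunnett Testing Method at a one-sided familywise error rate of 0.10". The synopsis repeats it without the word power: "at least 80% to detect a pairwise difference of 0.65 in mean WI-NRS change". Enrolment is set at about 576, or 192 per group, to allow for 16.7% dropout before study completion.

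Three other places bear on how to read the sentence.
- SAP 7.2.6 says that the mITT results "will be considered definitive for superiority of each active treatment to vehicle".
- SAP 7.4.2 tests each dose against vehicle with the Dunnett method and presents Dunnett-adjusted one-sided limits. Its ANCOVA model "will have treatment group and Baseline weekly average WI-NRS as explanatory variables".
- Protocol 11.6 ties completion to the whole visit schedule, with Day 56 as the last visit: "A completed participant is one who has completed all study visits".

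**The concern.** The sentence gives every input for a per-dose power calculation, so it can be checked directly, and the check does not return 80%. The sentence also leaves three things open: whether power means success on a given dose or on at least one dose, what effect the other dose is assumed to have, and whether SD 2.5 is the raw SD of change or the residual SD after baseline adjustment.

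This is the only justification of the sample size. Someone interpreting a non-significant dose would assume that a true 0.65 effect is missed at most 20% of the time.

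**Working it through.** **Inputs.** From SAP 7.1: n = 160 evaluable per arm, difference 0.65, SD 2.5, one-sided Dunnett with familywise error 0.10, dropout 16.7%. From SAP 4.1: 1:1:1 allocation, so the two dose-versus-vehicle contrasts share the vehicle arm and correlate at 0.5.

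**The plan's own figures.** The dropout step reproduces: 160/192 = 83.3%, and 576 × (1 − 0.167) = 479.8, or 480. The power does not.

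**Per-dose power at 160 per arm.**
1. SE of a pairwise difference = 2.5 × √(2/160) = 0.2795.
2. Non-centrality = 0.65 / 0.2795 = 2.326.
3. Single-step Dunnett critical value for two contrasts with correlation 0.5 and one-sided 0.10 = 1.577 (normal) or 1.580 (t, 477 df). The per-comparison alpha is 0.0574.
4. Power (normal) = Φ(2.3255 − 1.5770) = Φ(0.7485) = 0.7729. The non-central t gives 0.7721. A simulation of 500,000 trials gave 0.772, with a familywise error of 0.100.

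**Sample size for 80% per dose.** n = 2 × (2.5/0.65)² × (1.577 + 0.842)² ≈ 173.1, so 174. On the t distribution, 173 gives 0.7991 and 174 gives 0.8011. That is 14 more per arm than 160 (14/160 = 8.8%).

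**Other readings at 160 per arm.**

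| Reading | Power at 160 | n per arm for 80% |
|---|---|---|
| Given dose, single-step Dunnett | 77.2% (t), 77.3% (normal) | 174 |
| At least one dose, only one active | 77.3% (t), 77.4% (normal) | 173 (t) |
| At least one dose, both at 0.65 | 89.5% | 113 (normal), 114 (t) |
| Both doses, both at 0.65 | 65.0% | not computed |
| No multiplicity adjustment, one-sided 0.10 | 85.2% | 134 |
| Bonferroni, one-sided 0.05 each | 75.2% | 183 |

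None of these gives 160 as the number needed for 80%. For at-least-one-dose power to reach 80% at 160, with one dose at 0.65, the other must have an effect of about 0.34: an effect of 0.33 gives 0.799 and 0.35 gives 0.803.

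**Ranges under assumptions that the documents do not state.**
- *Baseline adjustment.* If 2.5 is the raw SD of change and r is its correlation with baseline, the residual SD is 2.5 × √(1 − r²). Per-dose power at 160 is then 78.6% for r = 0.20, 80.0% for r = 0.28 and 83.1% for r = 0.40.
- *Evaluable at Week 4.* The 16.7% runs to Day 56, so more than 160 of 192 may be evaluable at Week 4. Having 174 evaluable means a loss of 18/192 = 9.4% and gives 80%. No loss (192) gives 83%.

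**The case against.** The strongest reply is that power for one of two doses can be read as success on at least one dose. If both doses have the 0.65 effect, that power is 89.5% and the claim of at least 80% is true. A claim of at least 80% also does not require 160 to be the smallest sufficient number. In addition, the documents do not say whether the Dunnett method is single-step or step-down: with step-down and both doses at 0.65, per-dose power is 82.2%. SAP 7.2.6 mainly ranks the mITT population above the per-protocol population and does not define a power target. Finally, the gap is small: a difference of 0.68 or an SD of 2.4 would close it.

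Part of this stands. The power definition is missing, and the at-least-one-dose reading cannot be ruled out from the sentence alone. But that reading and the step-down reading both need an effect for the second dose, and none is stated. If the second dose has no effect, at-least-one-dose power is still 77.3%. If it has the full effect, 160 is far more than the number required. The Dunnett-adjusted one-sided limits in SAP 7.4.2 fit a single-step procedure better. The sentence speaks of a pairwise difference, the primary test is pairwise for each dose, and SAP 7.2.6 words the superiority conclusion dose by dose. Per-dose power is therefore the natural reading, though not the only possible one.

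**Conclusion.** The concern holds, as a minor error. With the stated inputs and a single-step Dunnett test, power for a given dose is about 77%, nearly 3 points below the stated figure. The chance of missing a true 0.65 effect on that dose is about 23%. Every route back to 80% at 160 evaluable per arm needs an input that the documents do not give: an effect of about 0.34 or more in the other dose, a step-down procedure with both doses active, or a baseline correlation of about 0.28. Lower loss at Week 4 would raise the evaluable number, but the plan states its power at 160.

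This is a wrong figure and an incomplete power statement, not a design flaw.

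**What to change.** Keep the sample size. In SAP 7.1, Protocol 12.1 and the synopsis, restate the power along these lines:

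> With 160 evaluable per group, power is about 77% for each comparison of a B244 dose with vehicle. If both doses have a 0.65 effect, it is about 89% for at least one dose and 65% for both.

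Add the power definition, the effect assumed for each dose, whether the Dunnett procedure is single-step or step-down, and whether SD 2.5 is baseline-adjusted. If the calculation used another input, such as a baseline correlation, give the value actually used and the power it yields. Do not choose a value after the fact to reach 80%.

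The cost is a few lines in three places, with no extra patients. The stated per-dose power falls to 77% unless a documented input supports more. For comparison, holding 80% per dose by sample size would need 174 evaluable per arm: 174/0.833 = 208.9, so 209 randomized per arm and 627 in total against 576. That increase is not proposed.
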